## 3. Participant Entry

Children with spastic cerebral palsy between the ages of 4 and 18 years that are due to start BTX-A treatment in their upper limb will be recruited for this study. If the child and parent/carer are happy to take part, the parent/carer will be consented prior to enrolment and will sign the parent-carer consent form. With regards to those over 16 years, they will also be assented prior to enrolment.

## 3.1 Inclusion Criteria

- 1. Participants must be aged between 4 and 18 years.
- 2. Participants must be diagnosed with spastic cerebral palsy in at least one of their upper limbs.
- 3. Participants must be due to start BTX-A treatment for their affected upper limb.
- 4. Participants must have minimum ability to hold an object and stabilise it for use by the other hand.
- 5. Participants must be able to comprehend and complete the test protocol.
- 6. Participant or the participants parent/carer must be able to speak, read and understand English, in order to be involved in this study.

## 3.2 Exclusion Criteria

- 1. Any surgical intervention on the upper extremity in the last 6 months.
- 2. Any known allergy to adhesives.

- 3. Any known skin allergies.
- 4. Unable to obtain informed consent from participant's parent/carer.
- 5. The participant and the participants parent/carer are not able to speak, read and understand English.

## 3.3 Withdrawal Criteria

Participants will be informed, both verbally and in writing, of their right to withdraw from the study at any time without the withdrawal affecting the standard of care they receive or any future interactions they may have with Imperial College London or the NHS Trust. If any participant wishes to be withdrawn from the study then the information collected with consent up until that point would be retained and used in the study; however, no further data will be collected regarding the participant.

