## 3.4 Sample size

Sample size: 8 healthy participants between the ages of 4 and 18.

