# 4. Study Design

## 4.1 Methodology

Participants will be asked to take part in all the tests listed below. This will take approximately 1 hour in total. The participants will attend three sessions at the 1st Floor, Paediatric Outpatients, Chelsea and Westminster Hospital ([name]). The first session being before they start BTX-A treatment, the second session will be between 3 weeks and 6 months after treatment and the third session will be at least 6 months after treatment. All the sessions will consist of the procedures described in sections 4.1.1, 4.1.2 and 4.1.3.

Upon arrival at the 1st Floor, Paediatric Outpatients Department, participants' carers will be asked to review the participant information sheet and sign the consent form, if they have not already done so. If the participant is over the age of 16 years of age, they will be asked to sign a consent form. For participants under the age of 16, they will sign an assent form. Demographic information regarding the participant's age (current year and month), diagnosis and any significant birth history or previous surgery will be documented. Participants must consent to the clinical care team

reviewing the ultrasound scan reports to ensure any incidental findings can be appropriately investigated and acted upon.

A camera with a tripod, will be used to video record future data processing. The participant will be seated at a table and the camera will be focused on the participant's upper extremity and the tabletop. For the best observation of participant's extremity, long hair will be restrained, if possible, and their sleeves will be rolled up above the elbow. The participant will be positioned sideways to the camera with uninvolved side closest to the camera and the involved side furthest from the camera. This position allows best visibility of the involved hand and thumb for the video.

Participants will be asked to take part in a series of three main activities: Shriners hospital upper extremity evaluation, ultrasound measurements and EMG measurements. Following each task, a 3-minute rest period will be designated in order to avoid the effects of fatigue.

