## 4.4 Outcome measures

Primary outcome measure: The primary outcome measures are the elasticity of the tendons and the anthropometrics of the muscles before and after BTX-A injections.

Secondary outcome measure: The secondary outcome measure is the comparison of computational models for data collected before and after BTX-A injections.

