## 6 Assessment and follow up

All ultrasound scans will be reported to and reviewed by the clinical care team so that in the event of incidental findings these can be appropriately investigated and acted upon.\_There will be no routine follow up for participants. The end of study is defined as the end of the third data collection session or the final data collection session for that participant.

The end of study is defined as the end of the third data collection session or the final data collection session for that participant.

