# 7. Statistics and data analysis

The sample size has been calculated using a power analysis calculation. The data will be analysed using Shapiro-Wilk test to test for normality. Depending on the results of the Shapiro-Wilk test, the data will be further analysed using t-tests and ANOVA tests for comparison of data.

Data and all appropriate documentation will be stored for a minimum of 10 years after the completion of the study, including the follow-up period.

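### Section 7 names t-tests and ANOVA without a within-child form; in their standard forms neither makes good use of the partial data that section 3.3 says will be used

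*Protocol*

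**What the plan says.** Section 4.4 defines the primary outcome as "the elasticity of the tendons and the anthropometrics of the muscles before and after BTX-A injections". Section 4.1 sets the schedule: "The participants will attend three sessions", one before treatment, one between 3 weeks and 6 months after it, and one at 6 months or later with no upper limit. Section 3.4 gives the number of children: "Sample size: 8 healthy participants between the ages of 4 and 18" (the word healthy there is a separate matter).

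Two places allow for a child with fewer than three sessions. Section 3.3 says that after withdrawal "the information collected with consent up until that point would be retained and used in the study" and that "no further data will be collected regarding the participant". Section 6 says: "The end of study is defined as the end of the third data collection session or the final data collection session for that participant".

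On analysis, section 7 (Statistics and data analysis) says that after a Shapiro-Wilk test "the data will be further analysed using t-tests and ANOVA tests for comparison of data". It does not say whether these tests are paired, repeated-measures or independent-sample. It also says "The sample size has been calculated using a power analysis calculation", without giving the inputs.

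**The concern.** A before/after outcome in the same children calls for a within-child comparison. The methods named in section 7 can be read in two standard ways, and each handles an incomplete child poorly.

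- **Within-child form.** A paired t-test of sessions 1 and 2 uses any child who has both. A standard repeated-measures ANOVA over three sessions keeps only children with all three, so a child who stops after session 2 loses two good measurements. The t-test and the ANOVA may then describe different children.
- **Independent-sample form.** Every measurement is kept, but the before and after means come from partly different children. With ages from 4 to 18 and muscle size among the outcomes, who is present can move a mean with no treatment effect. The pairing is also lost.

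With 8 children, one child is 1/8 = 12.5% of the sample. The protocol intends to use partial data, and the standard forms of its named tests either discard part of them or use them inefficiently.

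**Working it through.** **The plan's own figure.** The sample size of 8 cannot be reproduced, because no significance level, power, effect size, standard deviation or dropout rate is given. What follows is illustrative and its inputs are assumptions.

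**How likely is an incomplete child?** With dropout probability q per child, the chance of at least one among 8 is 1 − (1 − q)^8. For q = 5%, 10%, 20% and 30% this is 34%, 57%, 83% and 94%.

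**What is thrown away.** If k children miss session 3, 24 − k sessions are recorded and a complete-case ANOVA uses 3(8 − k).
- k = 1: 21 of 23 used
- k = 2: 18 of 22 used
- k = 3: 15 of 21 used

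**Effect on power.** Take the 2-degree-of-freedom F test for session at the 5% level, with equal correlation between sessions and within-child standard deviation σ. The noncentrality λ is a sum over children:
- a child with all three sessions adds a = Σ(μ_s − μ̄)²/σ²;
- a child with sessions 1 and 2 adds b = Δ₂²/(2σ²), where Δ₂ is the session 2 change.

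For 78% power with 8 complete children (error df 14), λ = 11.47, so a = 11.47/8 = 1.434.

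Complete-case ANOVA: λ = (8 − k)a, error df = 2(7 − k). All available sessions: λ = (8 − k)a + kb, error df = 14 − k. The ratio b/a depends on the course of the effect:
- half the session 2 change remains at session 3, means (0, Δ, Δ/2): a = Δ²/(2σ²), so b/a = 1;
- session 3 equals session 2, or returns fully to baseline: a = 2Δ²/(3σ²), so b/a = 0.75;
- change appears only at session 3: b = 0.

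| Children missing session 3 | Complete-case ANOVA | All available, b/a = 1 | b/a = 0.75 | b = 0 |
|---|---|---|---|---|
| 0 | 78% | 78% | 78% | 78% |
| 1 | 70% | 77% | 76% | 71% |
| 2 | 61% | 76% | 73% | 63% |
| 3 | 50% | 75% | 71% | 54% |

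A separate simulation of 8 children, with about 78% power on full data, gave about 72%, 61% and 50% for complete-case ANOVA against 78%, 77% and 75% for the all-available model, with type I error near 5% in both. That is close to the b/a = 1 column.

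**A child with session 1 only.** No method supplies this child's change. If 8 pairs give 80% power in a two-sided 5% paired t-test (standardised change 1.156), 7 pairs give 72% and 6 give 62%. A mixed model recovers little of that loss.

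**The case against.** The strongest objection is that rules for missing sessions, analysis sets and the exact form of a test are usually left to the statistical analysis plan, which may exist. That stands as far as mere silence goes. What remains is that the protocol itself names the methods, says partial data will be used and foresees early endings. ANOVA can also be read broadly enough to include a model with child as a factor on all available sessions. If that is meant, one sentence in section 7 settles the matter.

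Some stronger readings are tempting and are not supported:

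- *Sections 3.3 and 7 contradict each other.* Section 3.3 is mainly about consent and retention. Using the data in the study does not promise that each record enters every comparison. Retained data could serve description or the session 1 to session 2 comparison.
- *Section 6 counts an incomplete child as complete.* It only defines when the study ends and says nothing about analysis status.
- *Any child who stops early is lost to the before/after outcome.* Only a child with session 1 alone lacks a pair.
- *Dropout creates a spurious effect as large as the standard error.* If the child with the lowest value leaves after session 1, the expected shift in an unpaired mean is 1.424/7 = 0.20 between-child SD. That shift cannot arise in a paired analysis, so a paired standard error is the wrong yardstick. The unpaired one for 8 against 7 is √(1/8 + 1/7) = 0.52 SD. The protocol nowhere says that unpaired tests will be used.

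**Conclusion.** The point holds as a mismatch between method and design, worth correcting but not an inconsistency that undermines the study. Under the assumptions above, the complete-case ANOVA loses about 8, 17 and 28 percentage points of power when one, two or three of 8 children miss session 3. The all-available analysis loses about 1 to 3 points per two-session child when the effect is present at session 2 in the patterns tried. The advantage shrinks to between 1 and 4 points in total if the effect appears only at session 3.

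These figures rest on an assumed 78% power with full data, equal correlation between sessions, the 5% level and losses unrelated to the unobserved values. The dropout rate is unknown.

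**What to change.** Change section 7 only:

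- State that the comparison is the within-child change from session 1.
- Estimate it with a linear mixed model, session as a fixed effect and child as a random effect, fitted to all available sessions, with a small-sample degrees-of-freedom correction such as Kenward-Roger.
- Report the number of children with data at each session.

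The wording of sections 3.3 and 6 can stay as it is. A child with session 1 only will be in the model but will add little to the estimated change.

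The cost is a few sentences, with no extra children or procedures. The model assumes that sessions are missing at random, which is weaker than what a complete-case analysis generally needs. It also assumes a simple covariance structure, which 8 children cannot test well.

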## 3.4 Sample size

Sample size: 8 healthy participants between the ages of 4 and 18.

## 3.5 Recruitment

For this study, potential participants due to start BTX-A treatment are invited to take part in the study and their parent/carer will be invited to take part in this research study by their hand surgeon when they are due to start BTX-A treatment. If interested, the potential participant's parent/carer contact details will be passed on to the coinvestigator, ([name]) and they will be provided the participant information sheet and any further information.

# 4. Study Design

## 4.1 Methodology

Participants will be asked to take part in all the tests listed below. This will take approximately 1 hour in total. The participants will attend three sessions at the 1st Floor, Paediatric Outpatients, Chelsea and Westminster Hospital ([name]). The first session being before they start BTX-A treatment, the second session will be between 3 weeks and 6 months after treatment and the third session will be at least 6 months after treatment. All the sessions will consist of the procedures described in sections 4.1.1, 4.1.2 and 4.1.3.

Upon arrival at the 1st Floor, Paediatric Outpatients Department, participants' carers will be asked to review the participant information sheet and sign the consent form, if they have not already done so. If the participant is over the age of 16 years of age, they will be asked to sign a consent form. For participants under the age of 16, they will sign an assent form. Demographic information regarding the participant's age (current year and month), diagnosis and any significant birth history or previous surgery will be documented. Participants must consent to the clinical care team

reviewing the ultrasound scan reports to ensure any incidental findings can be appropriately investigated and acted upon.

A camera with a tripod, will be used to video record future data processing. The participant will be seated at a table and the camera will be focused on the participant's upper extremity and the tabletop. For the best observation of participant's extremity, long hair will be restrained, if possible, and their sleeves will be rolled up above the elbow. The participant will be positioned sideways to the camera with uninvolved side closest to the camera and the involved side furthest from the camera. This position allows best visibility of the involved hand and thumb for the video.

Participants will be asked to take part in a series of three main activities: Shriners hospital upper extremity evaluation, ultrasound measurements and EMG measurements. Following each task, a 3-minute rest period will be designated in order to avoid the effects of fatigue.

## 4.1.1 Shriners Hospital Upper Extremity Evaluation (SHUEE)

The SHUEE is designed to evaluate both functional and spontaneous abilities, as well as to document dynamic segmental alignment when performing tasks (11). During this session, nine different activities will be performed. Each activity will be verbally explained, and participants will be allowed to trial the required motion prior to the start of the recording. For each task, all items must be placed on table, presented at midline, without reference to which hand should be used unless otherwise noted.

#### Money from wallet task: (1 minute)

For this task the participant is presented with a closed billfold style wallet and is asked to remove the paper bills from inside the wallet. If the participant doesn't use their involved extremity, the participant will be asked to do the task again letting the other hand help. The evaluator will replace the money in the wallet and the participant will repeat the task.

## Fold piece of paper task: (1 minute)

For this task the participant is handed a plain sheet of paper and is asked to fold the paper in half in any fashion. If the participant doesn't use the involved extremity, the participant will be asked to do the task again letting the other hand help. The evaluator will flatten out the piece of paper and the participant will repeat the task.

#### Tear piece of paper task: (1 minute)

For this task the folded piece of paper is handed to the participant and is asked to tear the paper in two. The evaluator may initiate three tears and the paper does not have to be torn on the fold.

#### Unscrew bottle cap task: (1 minute)

For this task the participant is handed a screw cap bottle and is asked to remove the cap. The evaluator may loosen the cap and the cap does not have to be replaced by the participant. After participant completes the task, they will be asked to repeat it.

## Pull Play-Doh® apart task: (1 minute)

For this task the evaluator will mould the Play-Doh® into a cylindrical shape and the participant will be asked to pull the Play-Doh® apart at least three times.

## Accept coins/change task: (1 minute)

For this task the evaluator will give the participant three coins, placing them into the participants open palm. The participant should not use the table to facilitate supination so the participant can move away from the table for this task. If the participant doesn't use the involved extremity, the participant will be asked to do the task again using the other hand.

## Touch opposite ear task: (1 minute)

For this task the participant is asked to touch their contralateral ear with their palm. If the participant doesn't use the involved extremity, the participant will be asked to do the task again using the other hand.

## Place sticker on ball task: (1 minute)

For this task the participant is presented with a sticker and a ball and is asked to place the sticker on the ball. The ball is placed at arm's length from the participant to demonstrate elbow extension.

## Put sock on task: (1 minute)

For this task the participant should have one sock and one shoe removed. The participant will be asked to put their sock back on. If the participant doesn't use involved extremity, the participant will be asked to do the task again letting the other hand help.

#### 4.1.2 Shear-wave elastography ultrasound measurements

#### (20 minutes)

Shear-wave elastography (SWE) is a novel ultrasound technology for characterising mechanical properties of soft tissues through dynamic measurement of tissue displacement as a result of mechanical excitation. A LOGIQ E10 Ultrasound R2 system (GE Healthcare, Chicago, IL, USA) with a ML6-15-D probe (GE Healthcare, Chicago, IL, USA) will be used to collect SWE measurements including the shear-wave velocity during the relaxed and stretched states of the origin and insertion tendons of the muscles to be injected with BTX-A. As the shear modulus is equal to the shear-wave velocity multiplied by the density of the tissue, this will provide information regarding the elasticity of the tissue. In addition to this, the ultrasound measurements can provide tissue anthropometrics such as tissue length and cross-

sectional area. This will provide insight of the biomechanical adaptations after BTX-A treatment and how they contribute to joint function.

For this task the investigator will apply ultrasound gel between the probe and the participant's skin at the region of interest to limit tissue deformation caused by the operator. As the shear-wave velocity is dependent on the probe orientation relative to the muscle fibres, all the SWE acquisitions will be performed parallel to the direction of the muscle fibres and perpendicular to the participant's skin. When the ultrasound probe is correctly aligned, the shear-wave velocity and a sequence of 10 continuous images will be recorded. This will be repeated for the each of the muscles involved in the participant's BTX-A treatment.

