In order to build on the knowledge of the effects BTX-A has on the upper extremity, clinical hand assessments will be used in conjunction with biomechanical tools to investigate the mechanical and anthropometric adaptations. A novel technology, shear-wave elastography (SWE) will be used to evaluate the properties of muscles and tendons before and after BTX-A injections. The comparison of data collected before and after BTX-A treatment will inform the BTX-A induced adaptations. The data obtained from this study will be used to contribute to computational models in order to identify limits of suitability for a muscle or tendon to aid in surgical treatment.

This study will provide insight of the biomechanical adaptations of muscles and tendons after BTX-A treatment and how they contribute to joint function among a population of children with spastic CP. This will bring more understanding of the general behaviour of the musculoskeletal system following treatment which will benefit muscle and tendon selection for monitoring purposes or prospective surgical interventions and allow for a more objective guideline to be implemented.

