## Grasp and Release Analysis (GRA):

The GRA documents if the participant can or cannot grasp and release the object with the wrist in the three different positions. A yes (Y) or no (N) for grasp and release is provided contingent on the participants ability to close and open fingers with the wrist

maintained in each position. Video examples of optimal grasp and release for each position are available online.

The SWE images obtained will be processed using a custom software developed in MATLAB (The MathWorks, Natick, MA, USA) to process the images semiautomatically.

The EMG signals obtained will be processed using a custom software developed in MATLAB that will ensure the signal is low-pass filtered for noise, full wave rectified and smoothed.

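### Section 4.1.2 gives the shear modulus as velocity times density; the velocity must be squared, and tendon elasticity values would be wrong if the sentence is applied as written

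*Protocol*

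**What the plan says.** Protocol section 4.1.2 describes shear-wave elastography of the tendons of the muscles to be injected, at rest and under stretch. At each site, "the shear-wave velocity and a sequence of 10 continuous images will be recorded". The step from velocity to elasticity is given in words: "As the shear modulus is equal to the shear-wave velocity multiplied by the density of the tissue", and the sentence goes on to say that "this will provide information regarding the elasticity of the tissue". No density value is given.

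Section 4.4 makes elasticity a primary outcome: "The primary outcome measures are the elasticity of the tendons and the anthropometrics of the muscles before and after BTX-A injections". The secondary outcome is a model comparison: "The secondary outcome measure is the comparison of computational models for data collected before and after BTX-A injections". The Introduction adds: "The data obtained from this study will be used to contribute to computational models".

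Section 4.2, on data processing, says of the elastography only this: "The SWE images obtained will be processed using a custom software developed in MATLAB". It gives no formula.

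**The concern.** A modulus is a stress and is expressed in pascals. Velocity multiplied once by density does not have that dimension, so the stated relation lacks a square on the velocity. Because the relation is written in words, a superscript lost in text extraction cannot explain it.

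The sentence matters because nothing else in the protocol connects the recorded quantity to the elasticity outcome. Someone writing the processing step from this document would find one rule, and it is wrong. The resulting error would not be a constant multiplier. It would vary with the velocity itself, and so between visits, between tendons, and between the resting and stretched states. Any model that takes absolute stiffness from these values would inherit the error.

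**Working it through.** **Inputs.** The stated rule is from section 4.1.2. The protocol gives neither a density nor expected velocities, so the values below are assumptions: density ρ = 1,000 kg/m³ and velocity v from 2 to 15 m/s. The protocol attaches no numerical result to the rule, so there is no figure of its own to reproduce.

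**Step 1: units.**

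- Stated rule, ρ × v: (kg/m³)(m/s) = kg/(m² s). This is not a pressure.
- With the square, ρ × v²: (kg/m³)(m²/s²) = kg/(m s²) = Pa.

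No regrouping or change of units turns the first into the second.

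**Step 2: absolute values.** The two SI numbers differ by ρv²/ρv = v, whatever the density.

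| v (m/s) | ρv, kg/(m² s) | ρv² | Ratio of SI numbers |
|---|---|---|---|
| 2 | 2,000 | 4 kPa | 2 |
| 5 | 5,000 | 25 kPa | 5 |
| 10 | 10,000 | 100 kPa | 10 |
| 15 | 15,000 | 225 kPa | 15 |

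The two middle columns are in different units. The ratio only shows what would happen if the first were reported as though it were pascals. A density of 1,100 kg/m³ would raise both middle columns by 10% and leave the ratio unchanged.

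**Step 3: before-after change.** With fixed density, if velocity changes by a ratio r, the stated rule gives a relative change of r − 1 and the squared form gives r² − 1.

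| r | Stated rule | Squared form |
|---|---|---|
| 0.8 | -20% | 0.64 − 1 = -36% |
| 1.2 | +20% | 1.44 − 1 = +44% |
| 1.5 | +50% | 2.25 − 1 = +125% |

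The error does not cancel when visits are compared. The sign for each pair is kept, because squaring is increasing for positive v.

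**Step 4: effect on a paired test.** On the log scale, log(ρv²) = log ρ + 2 log v. Every within-participant difference and its standard deviation doubles, and the t statistic is unchanged. On the raw scale, v₁² − v₀² = (v₁ − v₀)(v₁ + v₀), so each participant's difference is reweighted and the t statistic can move. One simulated set of eight pairs (assumed baseline median 5 m/s with log SD 0.25, follow-up ratio median 0.85 with log SD 0.15) gave t = -5.98 both ways on the log scale. On the raw scale it gave -5.67 for velocity and -5.06 for velocity squared. This is a single illustration and does not predict the trial's result.

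**The case against.** The strongest reply is that the sentence gives a rationale for measuring velocity and is not an analysis instruction. It says why velocity is informative. Section 4.4 names elasticity without naming the shear modulus, and section 4.2 does not say how the software derives anything. This stands. A reader might infer that the primary outcome and the model inputs will be wrong, but the documents do not support that. No section says that the MATLAB code applies this sentence, or that moduli obtained this way are what the models receive. The Introduction speaks only of study data in general.

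Three further points also stand. Velocity is recorded, so a wrong conversion could be redone without another visit. With fixed density the stated product is velocity rescaled by a constant, so tests on it are valid tests of velocity; what fails is calling the result a modulus, with its size and percentage change. The muscle anthropometrics, the other part of the primary outcome, do not depend on the relation.

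None of this makes the sentence right. It sits in the methods, no other section corrects it, and it is the only link the protocol gives from the measurement to a primary outcome.

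**Conclusion.** The relation in section 4.1.2 is wrong; this follows from units alone. The consequence is conditional. If the rule is applied as written, elasticity values are off by a factor equal to the velocity (2 to 15 over the assumed 2 to 15 m/s). A 20% change in velocity would be reported as +20% or -20% where the modulus changes by +44% or -36%, and any model inputs taken from those values would be wrong as well. The percentages assume only a fixed density and a hypothetical 20% change in velocity.

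The error is recoverable, keeps the direction of each paired change, and leaves muscle length and cross-sectional area alone. It still needs correcting before elasticity is derived, because it misstates how a primary outcome follows from its measurement.

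**What to change.** Replace the clause in section 4.1.2 with: *the shear modulus is the tissue density multiplied by the square of the shear-wave velocity, assuming a homogeneous, isotropic, linearly elastic medium.* The assumption should be written out because it is only approximate for tendon. Section 4.1.2 itself notes that velocity depends on how the probe lies relative to the muscle fibres, which would not happen in an isotropic tissue.

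Check that the MATLAB processing uses the squared form with a fixed, stated density. Report shear-wave velocity (m/s) beside the modulus (kPa), so that the result can also be read without the assumption.

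The cost is one sentence, one check of the code and one extra column in the results. Velocity is already being recorded, so participants and visits are unaffected.
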